### 3.8 Secondary Efficacy Analyses

The secondary efficacy analyses will be performed for the FAS only. For each variable, the test for equivalence between two treatment groups will be carried out with the following specified statistical methods.

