3.9.1 Procedures for discontinuation of a subject from investigational product

At any time, subjects are free to discontinue investigational product or withdraw from the study (i.e., investigational product and assessments), without prejudice to further treatment. A subject that decides to discontinue investigational product will always be asked about the reason(s) and the presence of any adverse events. If possible, they will be seen and assessed by an Investigator(s). Adverse events will be followed up (See Section 6) and all study drugs should be returned by the subject.

Randomized subjects who discontinue the study prematurely should immediately stop taking investigational product and complete the procedures described for Visit 7 (End of Treatment Visit), as soon as possible but not later than 7 days after discontinuation of investigational product. DXA and CT measurement should be performed as described for Visit 7.

If a subject is withdrawn from study, see Section 3.10.

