4. STUDY PLAN AND TIMING OF PROCEDURES

Study is planned to be conducted according to plan described in [Table 1](#).

This study is a 52-week, multi-centres, randomized, parallel-group, open, Phase IV study. All subjects will be enrolled by recruiting centres (centres treating patients with T2DM). Each enrolled subject will be referred to DXA measurement and abdominal CT scan.

The objectives of the study cover measurements at baseline, 4, 12, 24, 36 and 52 weeks. The primary efficacy end-point is to evaluate the effect of dapagliflozin 10 mg daily in

Clinical Study Protocol
Drug Substance Dapagliflozin
Study Code D1690L00067
Version 3
Date 07 June 2016

combination with metformin compared to glimepiride in combination with metformin on body composition in Korean T2DM subjects after 52 weeks of oral administration of open-label treatment.

Subjects with T2DM and inadequate glycaemic control ($\text{HbA1c} \geq 7.0\%$ and $< 10.0\%$) with stable metformin monotherapy ≥ 1000 mg/day for at least 8 weeks prior to enrolment will be eligible to enter the study.

The recruiting investigator will be the main point of contact for the subject and also responsible for the documentation of study data within the eCRF. All subjects do DXA measurement and abdominal scan scheduled to coincide with Visit 2 and Visit 7.

Local evaluation of the DXA will be conducted.

Table 1 Study Plan detailing the procedures

Study weeks	Screening (Baseline)	Randomisation	Treatment					End of Therapy	Rescue Visit ²
	0wk (-7...0 days)	0wk	4wks (+/- 7 days)	12wks (+/- 7 days)	24wks (+/- 7 days)	36wks (+/- 7 days)	52wks (+/- 7 days)	Planned if needed	
Visit	1	2	3	4	5	6	7	R	
Informed consent	0								
Demography	0								
Physical Exam ¹	0		0	0	0	0	0	0	
Medical/Surgical History	0								
Diabetes History	0								
12 lead ECG	0						0		
Height	0								
Weight	0		0	0	0	0	0	0	
BMI calculation	0		0	0	0	0	0	0	
Waist circumflex	0		0	0	0	0	0	0	
Pulse, blood pressure (SPB/DBP)	0		0	0	0	0	0	0	
FBG	0		0	0	0	0	0	0	
HbA1C	0		0	0	0	0	0	0	
CBC	0		0	0	0	0	0	0	
AST/ALT/total bilirubin	0			0	0	0	0	0	
BUN/creatinine	0			0	0	0	0	0	
Na/K/Cl	0			0	0	0	0	0	

4.1 Screening: VISIT 1

Procedures will be performed according to the Study Plan, see [Table 1](#).

Patients will obtain information regarding the study and sign informed consent for the study before any study related procedures are initiated.

Consented patients will be assessed to ensure that they meet eligibility criteria.

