Drug accountability of investigational product and metformin will be conducted.

Investigational product and metformin will be dispensed.

In case of glimepiride group, glimepiride can be up titrated to 2 mg to maintain glycaemic control at the discretion of the investigator after evaluation of glycaemic control in subjects. Glimepiride can be also down titrated to mitigate recurrent hypoglycaemic events at the discretion of the investigator but 0mg is not allowed. If further hypoglycaemic events occur with meeting the discontinuation criteria after taking the 1mg glimepiride, subjects may be discontinued from investigational product.

All serious adverse events will be reported.

Adverse Events will be collected from subject actually taking the IP.

Subjects will discontinue the study if one major hypoglycaemic event or recurring minor hypoglycaemic events (any recurrent events of hypoglycaemia, as judged by the investigator, not meeting the definition of major hypoglycaemic event) occur.

Randomized subjects who discontinue the study prematurely should immediately stop taking investigational product and complete the procedures described for Visit 7.

4.4 End of Treatment: VISIT 7

Physical exam contains measurement of weight, waist circumflex, pulse and blood pressure. BMI calculation will be conducted.

12 lead ECG will be conducted.

Subjects will be followed for laboratory assessment of efficacy and safety according to study plan FBG, HbA1c, CBC, AST, ALT, total bilirubin, BUN, creatinine, electrolytes, total cholesterol, triglyceride, HDL-cholesterol, urinalysis, hsCRP, adiponectin. All laboratory assessment will be done in central laboratory.

Diet and life-style counselling will be given to the subject.

DXA and abdominal CT measurement will be conducted.

Concomitant medications will be checked.

Drug accountability of investigational product and metformin will be conducted.

Subject diary will be reviewed for hypoglycaemic events.

All serious adverse events and adverse events will be reported and followed up

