8.3 Definitions of analysis sets

8.3.1 Efficacy analysis set

Full Analysis Set (FAS)

The full analysis set will include all randomized subjects who receive at least one dose of study medication during the 52 week treatment period who have a non-missing baseline value and at least one post-baseline value for primary efficacy variable.

Whenever appropriate, missing values will be replaced by the last observation carried forward (LOCF) approach.

Whenever using the FAS, subjects will be presented in the treatment group to which they were randomized.

Per-Protocol Set (PPS)

The per-protocol set is a subset of the full analysis set consisting of subjects who do not violate the terms of the protocol, which may affect the efficacy endpoints significantly. All decisions to exclude subjects from the full analysis set to create the per-protocol set will be made prior to DB locking.

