#### **2.1.4 Full Analysis Set [FAS]**

The full analysis set [FAS] will include all RND subjects who received at least one dose of study medication during the 52 week treatment period and have a non-missing baseline value and at least one post-baseline value for primary efficacy variable (total body fat mass).

Whenever using the FAS, subjects will be presented in the treatment group to which they were randomized.

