#### **2.1.5 Per-Protocol Set [PPS]**

The per-protocol set [PPS] is a subset of the FAS consisting of subjects who do not violate the terms of the protocol, which may affect the efficacy endpoints significantly (relevant protocol deviators).

All decisions to exclude subjects from the FAS set to create the PPS set will be made prior to DB locking.

Whenever using the PPS, subjects will be presented in the treatment group to which they were randomized.

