### **3.1 General Principles**

All safety outcome summaries will be performed on the SAF whilst all efficacy analyses will be performed on FAS or PPS (PPS for sensitivity analyses of efficacy endpoints) unless otherwise stated. In addition to the formal presentation of results detailed in the following sections, all study data will be listed by centre, patient number and treatment group.

For continuous data, descriptive statistics will be presented for each treatment group and overall, which includes number of patients (n), mean, SD, median, maximum and minimum unless otherwise specified.

For categorical data, the frequency and percentage of patients in each category will be presented. Counts that are zero will be displayed as “0” and all percentages will be based on population size of each treatment group unless otherwise specified.

Data will be listed to the same accuracy as recorded in the eCRF. Mean and median summary statistics will be presented to one additional decimal place, whilst the standard deviation (SD) will be presented to two additional decimal places. Minimum and maximum values will be presented to the same accuracy as recorded on the eCRF.

The default significant level of statistical testing will be 5%; confidence intervals will be two-sided 95% and all tests will be two-sided, unless otherwise specified in the description of the analyses.

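### Secondary efficacy models are restricted to subjects with a DXA pair, so usable HbA1c, glucose, weight and blood pressure records are dropped for lack of a scan

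*SAP*

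**What the plan says.** Protocol 8.3.1 limits the FAS to randomised, dosed subjects "who have a non-missing baseline value and at least one post-baseline value for primary efficacy variable". SAP 2.1.4 repeats the rule and names total body fat mass as the variable.

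On scan timing, Protocol section 4 says: "All subjects do DXA measurement and abdominal scan scheduled to coincide with Visit 2 and Visit 7". For subjects who stop early, Protocol 3.9.1 adds: "DXA and CT measurement should be performed as described for Visit 7", within 7 days of stopping.

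On populations, SAP 3.8 says "The secondary efficacy analyses will be performed for the FAS only". SAP 3.1 sets the general rule that "all efficacy analyses will be performed on FAS or PPS", with the PPS for sensitivity work, and SAP 2.1.5 says "The per-protocol set [PPS] is a subset of the FAS".

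SAP 3.8.2 analyses HbA1c, fasting glucose, weight, waist, BMI, SBP and DBP by MMRM, using every observed visit without imputation. It analyses HbA1c <7.0% at Week 52 by logistic regression with LOCF. SAP 3.1.4 lets LOCF draw on all available data, including unscheduled and rescue visits.

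**The concern.** Whether a fat mass scan exists has no bearing on whether an HbA1c or weight record can be analysed. MMRM and LOCF were chosen because they can use incomplete records, yet the FAS rule first removes every incomplete record that lacks a scan.

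Precision on the non-DXA secondary endpoints is at stake. So is the arm comparison, if subjects who leave without a scan differ in outcome and leave at different rates in the two open-label arms. The documents neither show nor exclude that pattern.

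**Working it through.** **1. Tracing one subject through the plan.** Take a treated subject with HbA1c at Weeks 12, 24 and 36 who then withdraws consent.

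| Step | Source | Result |
|---|---|---|
| Further observation | Protocol 3.10.2 | None after consent withdrawal, so no exit scan |
| FAS membership | Protocol 8.3.1, SAP 2.1.4 | No post-baseline fat mass: out |
| PPS membership | SAP 2.1.5 | Subset of the FAS: out |
| MMRM and LOCF/logistic models | SAP 3.8, 3.8.2 | FAS: out |
| Observed-data responder check | SAP 3.8.3 | FAS: out |
| Gender-adjusted MMRM | SAP 3.8.3 names no set, so SAP 3.1 applies | FAS or PPS: out |

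The result is the same for a subject lost to follow-up, one who skips the exit scan, one without a baseline scan, and a completer who missed only the Week 52 scan. An early leaver who has the exit scan stays in. The instruction to use all observed visits can be read as applying within the FAS, so the text is not strictly contradictory.

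**2. LOCF.** The scan that admits a subject is taken at Visit 7 or exit, where HbA1c is also drawn (Protocol 4.4). SAP 3.1.3 presents exit data with the end-of-treatment visit. If exit HbA1c counts as Week 52, few FAS members need LOCF and most subjects who do need it are outside the FAS. If it does not count, LOCF still serves early leavers who had the exit scan.

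**3. Size.** The plan has no figure to reproduce: no expected number without a DXA pair is available, and the sample size sections are redacted. What follows is illustrative, for HbA1c only.

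*Assumptions.* 60 per arm (120 randomised 1:1) and no true difference. Baseline HbA1c has mean 8.0 and SD 0.7, clipped to 7–10. Change at Weeks 12, 24, 36 and 52 has mean −0.6, slope −0.4 on baseline, between-subject SD 0.6 and residual SD 0.4. Within-subject correlation is ρ = 0.36/(0.36 + 0.16) = 0.69. Loss without a scan occurs after Week 12, 24 or 36.

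*Counts.* 120p for p = 2.5%, 5%, 10%, 15% gives 3, 6, 12, 18 subjects. Each has one, two or three values, about two on average, so about 6, 12, 24 and 35 post-baseline HbA1c values are left out.

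*Standard error at Week 52.* √(0.52 × 2/60) = 0.132 with nobody lost; √(0.52 × 2/51) = 0.143 at 15% loss, FAS only.

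*Random loss, variance.* FAS-only variance is proportional to 1/(1−p). All-data variance is the Week 52 diagonal element of the inverse of (1−p)Σ⁻¹ + (p/3)(J₁ + J₂ + J₃). Here Σ is the 4×4 correlation matrix with common correlation ρ, and Jₖ is the inverse of its first k rows and columns, padded with zeros. The ratio of FAS-only to all-data variance is:

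| ρ | 5% | 10% | 15% |
|---|---|---|---|
| 0.5 | 1.016 | 1.033 | 1.051 |
| 0.69 | 1.028 | 1.058 | 1.091 |
| 0.8 | 1.036 | 1.075 | 1.117 |

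Simulation at ρ = 0.69 gave 1.026, 1.053 and 1.086. At Week 12, or for completers missing only a scan, the ratio is 1/(1−p): 1.053, 1.111, 1.176.

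*Outcome-related loss, shift.* 4000 trials per scenario, with a logistic hazard of loss on the last observed HbA1c. The all-data estimate is the likelihood estimate for monotone missing data; the FAS-only estimate is Week 52 ANCOVA in subjects not lost. Entries are FAS-only minus all-data for dapagliflozin minus glimepiride:

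| Loss pattern | 2.5% | 5% | 10% | 15% |
|---|---|---|---|---|
| Unrelated to HbA1c | 0.000 | 0.000 | 0.000 | 0.000 |
| Related, same in both arms | 0.000 | 0.001 | 0.001 | 0.001 |
| Related, 2:1 rate, more on dapagliflozin | −0.006 | −0.012 | −0.024 | −0.036 |
| Related, 2:1 rate, more on glimepiride | +0.006 | +0.013 | +0.026 | +0.039 |
| Opposite directions by arm | −0.018 | −0.036 | −0.071 | −0.108 |

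The Monte Carlo error of these differences is at most 0.001. The last row is an adverse case that the documents do not support; a steeper dependence takes it to −0.152 at 15% loss. Responder rates and the other endpoints were not simulated.

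**The case against.** The strongest reply is that this is a choice of analysis set, made consistently in both documents. One population keeps fat mass, weight and HbA1c comparable in a body-composition trial. Secondary results are only descriptive (SAP 3.1.6). That is fair, and it limits the weight of the point, but it gives no reason to discard valid randomised data.

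Second, the exits most plausibly linked to glycaemia are those the protocol manages. Rescue can keep a subject in the trial, and protocol-directed discontinuation leads to Visit 7 procedures including DXA. This stands: many outcome-related leavers should remain in the FAS. The residual group is consent withdrawals, losses to follow-up and missed scans.

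Third, the simulation favours the alternative by construction. Loss depends on observed HbA1c, so the all-data estimate is unbiased. If withdrawal depended on unobserved values, both analyses would be biased. A subject lost before the first post-baseline HbA1c contributes none under either set. Both points stand and would weaken the HbA1c illustration; neither alters the trace.

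Fourth, the data do not vanish. HbA1c, glucose and blood pressure are listed on the safety set, and weight, BMI, waist and blood pressure are summarised there by visit (SAP 3.9.5). The disposition table in SAP 3.2 gives safety-set and FAS counts and reasons for discontinuation. True, but HbA1c and glucose have no safety-set summary of efficacy by visit specified in 3.8.2, no model recovers the subjects, and no table sets reason against FAS exclusion by arm.

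**Conclusion.** The concern holds. As written, a treated subject without a DXA pair enters none of the secondary efficacy models, and no sensitivity analysis restores that subject. This follows from the text and rests on no assumption.

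The consequence is probably modest and cannot be sized from the documents. Under the assumptions shown, some precision is always lost: at Week 52, 3% to 9% in variance for 5% to 15% random loss. Bias appears only if loss without a scan is related to outcome and differs between arms, and is then 0.01 to 0.04 HbA1c points for a 2:1 loss rate over the same range. Equal outcome-related loss in both arms gives essentially no shift. The primary analysis is untouched. The change should be made because it is cheap and removes a selection that serves no purpose for these endpoints, not because bias has been shown.

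**What to change.** - **SAP 2.1.4 and 3.8:** analyse each non-DXA secondary endpoint on all randomised, treated subjects with a baseline and at least one post-baseline value of that endpoint, in the randomised arm. Include HbA1c <7.0% and its comparison of LOCF with observed data. Keep the DXA requirement for fat mass and lean mass. The DXA-based FAS can stay as a sensitivity analysis.
- **SAP 3.2:** add a count, by arm and reason, of treated subjects outside the FAS. This would show directly whether the issue matters in this trial.
- **SAP section 4:** record the departure from Protocol 8.3.1; the section currently declares no changes.

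No new data are needed. The cost is that denominators will differ between tables, and SAP 2.1.4, 3.1, 3.2, 3.3, 3.8 and 3.8.3 must be aligned, because the same FAS is the protocol's efficacy set.

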#### 3.8.1 Secondary Efficacy Variables

There are multiple secondary efficacy variables of interest, as following:

The change in HbA1c levels from baseline to 52 weeks, which is defined as the HbA1c level measured at Week 52 (12, 24, 36 and 52 weeks) subtracts the subject's baseline value.

The proportion of subjects achieving a glycemic response, defined as HbA1c <7.0% at Week 52.

The change in FBS levels from baseline to 52 weeks, which is defined as the FBS level measured at Week 52 (4, 12, 24, 36 and 52 weeks) subtract the subject's baseline value.

The changes in body weight, waist circumference, BMI from baseline to 52 (4, 12, 24, 36 and 52) weeks, which is defined as the corresponding results measured at Week 52 (4, 12, 24, 36 and 52) subtract the subject's baseline value.

The changes in SBP and DBP from baseline to 52 (4, 12, 24, 36 and 52 weeks), which is defined as the results measured at Week 52 (4, 12, 24, 36 and 52 weeks) subtract the subject's baseline value.

The changes in abdominal VAT and SAT area, VAT/SAT ratio using abdominal CT from baseline to 52 weeks, which is defined as the results measured at Week 52 subtract the subject's baseline value.

The changes in lean mass using Dual Energy X-ray Absorptiometry (DXA) from baseline to 52 weeks, which is defined as the results measured at Week 52 subtract the subject's baseline value.

The changes in high-sensitivity CRP (hsCRP) and adiponectin from baseline to 52 weeks, which is defined as the results measured at Week 52 subtract the subject's baseline value.

### 3.8.2 Primary Analysis of Secondary Endpoints

To evaluate the difference between two treatment groups regarding change in HbA1c levels from baseline to 52 weeks (12, 24, 36 and 52 weeks), the following hypothesis will be tested:

$$H_0: \mu_T = \mu_C \text{ Versus } H_A: \mu_T \neq \mu_C$$

Where  $\mu_T$  denotes the mean change in test results from Baseline to Week 52 of subjects received Dapagliflozin (Treatment under investigation, T) and  $\mu_C$  denotes the mean change in test results from Baseline to Week 52 (12, 24, 36 and 52 weeks) of subjects received Glimepiride (Comparator, C).

The secondary variable will be analysed using a Mixed effect Model Repeat Measurement (MMRM) model with treatment group, visit, visit\*treatment group and baseline measurement as factors, as following:

$$E(Y_{ijk}) = \beta_0 + \beta_1 Trt_i + \beta_2 V_j + \beta_3 Trt_i \times V_j + \beta_4 Base_{ik}$$

Where  $i=1, 2$ ;  $j=1,2,\dots,5$ ;  $k=1, 2,\dots, n_i$ .

$E(Y_{ijk})$  denotes the change in test result from baseline to the  $j^{\text{th}}$  visit post-baseline of the  $k^{\text{th}}$  subject in treatment group  $i$ .

$Trt_i$  denotes the treatment effect of each group.

$V_j$  denotes the  $j^{\text{th}}$  visit post-baseline.

$Trt_i \times V_j$  denotes the interaction term of treatment group and visit.

$Base_{ik}$  denotes the baseline test result of  $k^{\text{th}}$  subject in treatment group  $i$ .

The above model will be applied to analyse the secondary efficacy endpoints. All non-missing visit data will be used. The model will be used to derive a least squares estimate of the treatment difference with a 95% CI and corresponding Wald two-sided p-value. Missing data will not be imputed.

The following SAS code can be used to obtain the above statistics:

```
proc mixed data=DATA; where AVISITN in (X,X,X,X) and  
PARAMCD="XXX";  
class TRTP AVISIT USUBJID;  
model AVAL=TRTP | AVISIT Base/solution;  
repeated AVISIT/type=un subject=usubjid r rcorr;  
lsmeans TRTP*AVISIT/diff=CONTROL('Comparator' 'Week52') cl;
```

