8.5.2 Analysis of the secondary variable(s)

The statistical significance levels for secondary endpoints will not be adjusted for multiple hypothesis testing and will be interpreted only descriptively

Change in HbA1c Levels from Baseline to 52 Weeks

Change from baseline to each visit measurement for HbA1c will be analyzed by a MMRM method. All non-missing visit data will be used. The model will include terms for treatment group, visit, visit*treatment group and baseline measurement as a covariate. The model will be used to derive a least squares estimate of the treatment difference with 95% confidence interval and corresponding two-sided p-value. Missing data will not be imputed.

Change in Body Weight, Waist Circumference, BMI from Baseline to 52 Weeks

For change in body weight, waist circumference, BMI from baseline to 52 weeks, a same manner of secondary efficacy variable (HbA1c) will be performed.

Change in SBP and DBP from Baseline to 52 Weeks

For change in SBP and DBP from baseline to 52 week, a same manner of secondary efficacy variable (HbA1c) will be performed.

The Proportion of Subjects Achieving a Glycemic Response, Defined as HbA1c<7.0% at Week 52

The proportion of subjects who achieved an HbA1c<7.0 at week 52 (LOCF) will be assessed using logistic regression analysis with treatment group as a factor and baseline HbA1c as a covariate.

The number and percentage of responders and non-responders will be also presented. The odds ratio and its 95% CI from logistic regression will be estimated.

Change in FBS Levels from Baseline to 52 Weeks

For change in FBS from baseline to 52 week, a same manner of secondary efficacy variable (HbA1c) will be performed.

Change in Abdominal VAT and SAT Volume, VAT/SAT Ratio Using Abdominal CT from Baseline

For change in abdominal VAT and SAT volume, VAT/SAT ratio using abdominal CT from baseline to 52 week, a same manner of primary efficacy variable will be performed.

Changes in lean mass from baseline using Dual Energy X-ray Absorptiometry (DXA) scan from baseline to 52 weeks)

For changes in lean mass from baseline using Dual Energy X-ray Absorptiometry (DXA) scan, a same manner of primary efficacy variable will be performed.

Change in hsCRP and Adiponectin from baseline to 52 Weeks

For change in hsCRP and adiponectin from baseline to 52 week, a same manner of primary efficacy variable will be performed.

Safety Analysis

All safety analysis will be based on safety analysis set.

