### **3.1.3 Retests, Unscheduled Visits, Early Termination Data and Rescue Visit**

In the case of a retest, a visit-specific unscheduled assessment will be created. The latest available measurement within the protocol specified +/- 7 days visit window will be used for by-visit summaries.

Unscheduled measurements (unless assigned to a planned visit number as described in the paragraph above) will not be included in by-visit table summaries and by-visit graphs, but will contribute to the last observation carried forward (LOCF) values described in SAP Section 3.1.4 and also contribute to baseline selection as described in Section 3.1.1.

Subjects who prematurely discontinue the study treatment will complete the same assessments as Visit 7 (End of Treatment Visit), and will not be further followed. Early termination data will be summarized and presented together with End of Treatment (EoT) Visit.

Randomized subjects with a central laboratory Fasting Blood Glucose (FBG) and HbA1c value meeting the criteria for lack of glycaemic control during treatment period may be eligible to receive open-label, prescribed rescue medication which may allow the subject to remain in the trial. Randomized subjects who meet the repeated rescue criteria should be scheduled for a rescue visit. Similar to unscheduled measurements, rescue visit results will not be included in by-visit table summaries but will contribute to LOCF algorithm.

Listings will include all scheduled, unscheduled, rescue visit, retest and early discontinuation data collected in the CRF without any unscheduled visit window mapping to scheduled visits.

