### **3.8.3 Sensitivity Analysis of Secondary Endpoints**

To assess the robustness of the missing data imputation (LOCF), the same model and statistics will be generated for FAS population with only truly observed data when evaluating proportion of subjects achieving a glycemic response.

To evaluate the impact of protocol compliance on secondary efficacy endpoint, secondary efficacy models (with imputed data for glycemic response) method will be repeated on the PPS population.

To evaluate the impact of gender ratio on secondary efficacy endpoints, the secondary endpoints will be analyzed as a sensitivity analysis by a mixed model for repeated measures (MMRM) where all post-baseline secondary endpoints (HbA1c levels, FBS levels, body weight, waist circumference, BMI, SBP and DBP) obtained at all planned visits before discontinuation from randomized treatment and visit and treatment are included as fixed factors and Baseline secondary endpoints and gender as covariates. Furthermore, interaction terms of visit by treatment, visit by gender and visit by respective Baseline secondary

endpoints will be included. An unstructured covariance matrix for respective Baseline secondary endpoint measurements within same patient will be employed. Regarding missing data this analysis approach relies on the assumption that data are missing at random. The estimated differences between each treatment groups at Week 52 and corresponding two sided p-values and 95% CI will be presented.

To evaluate the impact of gender ratio on secondary efficacy endpoint VAT/SAT area, VAT/SAT ratio and total body lean mass, these parameters will be analysed using ANCOVA model with treatment group as factor and Baseline test results and gender as a covariate on FAS and PPS population. The statistical modelling and analysis will be performed in the same manner as the primary efficacy variable using an ANCOVA model (Sensitivity Analysis).

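### The gender sensitivity MMRM in SAP 3.8.3 also changes the baseline terms and the data, so a shift from the main result cannot be attributed to gender

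*SAP*

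**What the plan says.** **Main MMRM.** Protocol 8.5.2 fixes the terms: "The model will include terms for treatment group, visit, visit*treatment group and baseline measurement as a covariate". SAP 3.8.2 follows it with the statement "model AVAL=TRTP | AVISIT Base/solution" and an unstructured covariance, "repeated AVISIT/type=un subject=usubjid r rcorr". On data it says "All non-missing visit data will be used". Treatment, visit and their interaction are in the model, with a single baseline slope shared by all visits.

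**Gender MMRM.** SAP 3.8.3 introduces a second MMRM for the same seven endpoints. The only purpose it gives is the impact of gender ratio, which is also the reason in the SAP amendment history. The model has "Baseline secondary endpoints and gender as covariates", plus "interaction terms of visit by treatment, visit by gender and visit by respective Baseline secondary" endpoint values. Its data are those "obtained at all planned visits before discontinuation from randomized treatment". The covariance is again unstructured.

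**Early stoppers.** SAP 3.1.3 has subjects who stop early complete the Visit 7 assessments and then leave follow-up. It adds: "Early termination data will be summarized and presented together with End of Treatment (EoT) Visit". It does not say whether those values enter the main MMRM as Week 52.

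**Gender ANCOVA.** For fat mass (SAP 3.7.3), and for VAT and SAT area, their ratio and lean mass (SAP 3.8.3), the gender analysis is the main ANCOVA with gender added and nothing else changed.

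**The concern.** A sensitivity analysis answers its question when it differs from the main analysis only in the feature under test. The gender MMRM also differs in how baseline is adjusted and in which visits are used. If its Week 52 difference moves away from the main result, three explanations compete: gender, the freed baseline slope and the excluded data. If the two results agree, opposite shifts may have cancelled.

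The data restriction could matter for the treatment comparison itself. Protocol 3.9 lists hypoglycaemic events among the reasons for stopping the investigational product, and Protocol 1.1 describes hypoglycaemia as a frequent sulfonylurea side effect. Early stopping may therefore differ by arm, and leaving those subjects' final values out could move the treatment difference for reasons unrelated to gender. At stake is whether the report can say anything specific about gender for these seven endpoints.

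**Working it through.** **1. The two models side by side**

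| Feature | Main MMRM (3.8.2) | Gender MMRM (3.8.3) | Part of the gender question? |
|---|---|---|---|
| Treatment, visit, interaction | yes | yes | unchanged |
| Covariance | unstructured | unstructured | unchanged |
| Gender | no | yes | yes |
| Visit-by-gender | no | yes | yes |
| Visit-by-baseline | no | yes | no |
| Data | all non-missing visits | planned visits before discontinuation | no |

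There are four differences. Two are the intended adjustment and two are extraneous.

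**2. Reach of the data restriction.** SAP 1.2 and 3.1.3 end follow-up at the End of Treatment visit. Protocol 3.9.1 places that visit no later than 7 days after stopping. The restriction therefore chiefly removes the early-termination visit, and it bites at Week 52 only if the main model counts that visit as Week 52. Its size cannot be computed from the documents.

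**3. Size of the visit-by-baseline change.** There is no plan figure to reproduce: the sample-size text is redacted, and no SD, slope, correlation or dropout rate is given for any MMRM endpoint. From the documents: 120 subjects, randomised 1:1; four post-baseline visits for HbA1c and five for FBG and weight. Everything else is assumed: 15% random monotone dropout, half the subjects of each gender, no true treatment difference, and residual correlation rho^|lag| between visits.

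- HbA1c-like: baseline SD 0.75, residual SD 0.6 to 0.8, rho 0.7, gender difference 0.15 at Week 52.
- Weight-like: baseline SD 12 kg, residual SD 1.2 to 3.6, rho 0.85, gender difference 0.8.
- FBG-like: baseline SD 35 mg/dL, residual SD 25 to 32, rho 0.5, gender difference 4.

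Each scenario had 400 runs, fitted by maximum likelihood with unstructured covariance. The fits were the main model (A), A plus gender and visit-by-gender (B), A plus visit-by-baseline (A2), and all terms (C). The data restriction was not simulated. Columns 3 and 4 are the SD, across runs, of the shift in the Week 52 treatment estimate.

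| Scenario | Slope of change on baseline, first to last visit | Gender terms (A to B) | Visit-by-baseline (B to C) | Ratio | SE ratio A/A2 |
|---|---|---|---|---|---|
| HbA1c, equal | -0.60 throughout | 0.0221 | 0.0122 | 0.55 | 1.000 |
| HbA1c, modest | -0.45 to -0.60 | 0.0207 | 0.0194 | 0.94 | 1.006 |
| HbA1c, large | -0.30 to -0.70 | 0.0222 | 0.0464 | 2.09 | 1.035 |
| Weight (kg) | -0.01 to -0.05 | 0.0930 | 0.1375 | 1.48 | 1.010 |
| FBG (mg/dL) | -0.35 to -0.60 | 0.8524 | 1.1732 | 1.38 | 1.012 |
| FBG, extreme | -0.20 to -0.80 | 0.8470 | 2.6477 | 3.13 | 1.076 |

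In four of six scenarios the non-gender term moves the estimate more than gender does. The total shift (A to C) is modest against the main model's SE: from 0.0262/0.1536 = 17% (equal slopes) to 2.7061/6.6954 = 40% (FBG, extreme).

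**4. Is the single slope itself a problem?** In large samples, the variance inflation at Week 52 is 1 + (d × SD_base/SD_resid)², where d is the true Week 52 slope minus the common slope. With equal SDs:

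- d = 0: 1.00, SE ratio 1.000
- d = 0.1: 1.01, SE ratio 1.005
- d = 0.2: 1.04, SE ratio 1.020
- d = 0.3: 1.09, SE ratio 1.044
- d = 0.5: 1.25, SE ratio 1.118

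The simulated SE ratios (1.000 to 1.076) lie within this range. For bias, the main model's mean estimate under a true difference of zero was between -0.0069 and 0.0056 for HbA1c, 0.0295 kg for weight, and 0.0477 and -0.1606 mg/dL for FBG. Each is within one Monte Carlo standard error (empirical SD/√400; for example 0.152/20 = 0.0076 and 6.81/20 = 0.34).

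**The case against.** The sponsor can fairly say five things.

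- **The main model is prespecified.** Its terms are those of Protocol 8.5.2, and randomisation protects the comparison. This stands. A reader might infer that the single slope is an error, or that the seven endpoints lose material precision at Week 52. The documents do not support that: they give no slopes or correlations, and the loss is zero if slopes are equal across visits.
- **Gender and visit-by-gender belong together.** This stands. A reader might count four confounding changes, but only two are extraneous.
- **The data restriction is narrow.** Largely true, since there is no follow-up after End of Treatment. It can still act at the visit of interest, because SAP 3.1.3 leaves the status of early-termination values in the MMRM open.
- **Gender is already isolated where it matters most.** True for the primary endpoint, VAT and SAT, and lean mass. It does not help the seven MMRM endpoints, for which no gender-only model is planned.
- **The tests are descriptive** (SAP 3.1.6; Protocol 8.5.2). This stands and sets the priority. A descriptive analysis should still address the question it was added to answer.

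**Conclusion.** The attribution problem follows from the text alone. The gender MMRM alters the baseline adjustment and the data as well as gender, so a shift from the main result has no single explanation.

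The size is conditional. Under the assumed inputs, visit-by-baseline moved the Week 52 estimate by 0.55 to 3.1 times as much as the gender terms. The effect of the data restriction is unknown and would add to this. Total movement stays well below one standard error in every scenario.

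The main MMRM is not at fault. Leaving visit-by-baseline out of it costs nothing if slopes are equal, about 1% of Week 52 confidence interval width under modest change and about 4% to 8% under large change, all on assumed slopes. No primary conclusion depends on any of this. It is a cheap improvement, not a defect that threatens the trial.

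**What to change.** In SAP 3.8.3, define the gender MMRM as the 3.8.2 model on the same data, with the same baseline terms and the unstructured covariance both models already use. Add `gender` and `gender*AVISIT` and nothing else. Report the restriction to visits before discontinuation as a separate run, and state in 3.1.3 or 3.8.2 whether early-termination values count as Week 52 in the MMRM.

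Put visit-by-baseline in both models or in neither:

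- **Neither** needs no departure from Protocol 8.5.2.
- **Both** costs 3 degrees of freedom for HbA1c (four visits) and 4 for the other six endpoints (five visits). It may narrow the Week 52 interval. It should be decided before database lock and recorded in SAP section 4, which now lists no changes from the protocol.

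The cost is one extra run for the seven endpoints and a few lines of SAP text.
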